[Table 3](#) and [Table 4](#) display the preliminary lists of diseases, conditions, and procedures mapped to the ICD-10-CM codes for identification of the current approved indications. ICD-10-CM codes are used in the Danish national databases and in Cegedim (France); Read codes and ICD-10-CM codes are used in the CPRD (UK). These lists of codes will be used to identify the group of on-label users of dabigatran etexilate in each population. The complete list of codes will be available in the detailed, database-specific study protocol.

Two levels of on-label use will be investigated:

- The first level will include a broad definition based on the main code(s) for the approved clinical indications, e.g., atrial fibrillation.
- The second level will include a more restrictive definition by excluding patients with conditions for which the medication might not be indicated within the broad definition, e.g., valvular heart disease or low-risk patients with non-valvular atrial fibrillation.

Table 3 Preliminary list of diagnoses and corresponding ICD-10-CM codes for identification of new users of dabigatran etexilate for primary prevention of venous thromboembolism following total hip or knee replacement surgery

Disease/condition or procedure	ICD-10-CM description	ICD-10-CM code	Use of codes in indication definitions
Total hip replacement	Presence of artificial hip joint	Z96.64*	Primary code for the broad definition of the clinical indication
Total knee replacement	Presence of artificial knee joint	Z96.65*	Primary code for the broad definition of the clinical indication
Absence of venous thromboembolism between total hip or knee replacement surgery and dabigatran etexilate initiation **	Phlebitis and thrombophlebitis of femoral vein Phlebitis and thrombophlebitis of other and unspecified deep vessels of lower extremities Acute embolism and thrombosis of deep veins of lower extremity Pulmonary embolism	I80.1*; I80.2*; I82.3*; I26*	Sub-group of codes for exclusion of VTE in the restrictive definition within the clinical indication

* = wild card character indicating additional subcodes under this primary code; ICD-10-CM = International Statistical Classification of Diseases and Related Health Problems, 10th Revision, Clinical Modification, 2014 version. VTE = venous thromboembolism. Procedural codes will be included based on the dictionary system in place in each database.

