** Primary prevention defined as prevention of the first VTE event after the index surgery:

Table 4 Preliminary list of diagnoses and corresponding ICD-10-CM codes to identify on-label and off-label use for stroke prevention in non-valvular atrial fibrillation with dabigatran etexilate

Disease/condition or procedure	ICD-10-CM description	ICD-10-CM code	Use of codes in indication definitions
Atrial fibrillation	Atrial fibrillation and flutter	I48*	Primary code for the broad definition of the clinical indication
Valvular heart disease	Non-rheumatic mitral valve, aortic valve, tricuspid valve, pulmonary valve disorders Endocarditis, valve unspecified Endocarditis and heart valve disorders in diseases classified elsewhere	I34*- I39*	Sub-group of exclusive codes for the restrictive definition within the clinical indication
	Chronic rheumatic heart diseases	I05*-I08*, I09.1	Sub-group of exclusive codes for the restrictive definition within the clinical indication
	Congenital malformations of pulmonary and tricuspid valves Congenital malformations of aortic and mitral valves	Q22*-Q23*	Sub-group of exclusive codes for the restrictive definition within the clinical indication
	Presence of heart valve replacement Presence of xenogenic heart valve	Z95.2* - Z95.4*	Sub-group of exclusive codes for the restrictive definition within the clinical indication

Table 4 (cont'd) Preliminary list of diagnoses and corresponding ICD-10-CM codes to identify on-label and off-label use for stroke prevention in non-valvular atrial fibrillation with dabigatran etexilate

Disease/condition or procedure	ICD-10-CM description	ICD-10-CM code	Use of codes in indication definitions
	Mechanical complication of heart valve prosthesis Mechanical complication of coronary artery bypass graft and biological heart valve graft Infection and inflammatory reaction due to cardiac valve prosthesis	T82.0* T82.2* T82.6*	Sub-group of exclusive codes for the restrictive definition within the clinical indication
Stroke, transient cerebral ischaemia (TIA)	Cerebral infarction; occlusion and stenosis of pre-cerebral or cerebral arteries; TIA; acute, but ill-defined, cerebrovascular disease; sequelae of cerebral infarction	I63*-I66* I69.3* G45	Secondary code to support clinical indication
Symptomatic heart failure	Heart failure	I50*	Secondary code to support clinical indication
Systemic embolism	Arterial embolism and thrombosis	I74*	Secondary code to support clinical indication

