3.5.2 Off-label use definition

The definition of off-label use of oral dabigatran etexilate outside AF will be based on the use for a disease or medical condition other than the labelled indications and patient sub-groups given in Section [3.5.1](#). The dabigatran indications approved at the time of the index date will be used to define off-label use for each new user identified in the study period. In the absence of labelled indications, potential off-label use could include, but is not limited to, the following:

- General thrombosis prophylaxis other than hip and knee orthopaedic surgery.
- Treatment of deep vein thrombosis (DVT) and pulmonary embolism (PE) and prevention of recurrent DVT and PE in adults (CHMP opinion 25 April 2014), until Commission Decision
- Anticoagulation for patients with heart valve replacement or a stent.
- General prophylaxis or treatment of a thrombus in any site.
- Patients with hypercoagulability (e.g., factor V Leiden thrombophilia).

A preliminary list of ICD-10-CM codes to identify these conditions is provided in [Table 5](#). The final list will be included in the detailed, database-specific study protocol. In addition, the set of algorithms to be used as proxies for identification of potential clinical indications will be defined and described in the detailed, database-specific study protocol. These proxies will be based on codes for the presence of certain diseases and clinical conditions and the use of certain medications (e.g., use of other oral anticoagulants).

Because dabigatran etexilate has been approved for use only in adults, any identified use in the pediatric groups of age will be considered off-label. New users of dabigatran etexilate aged younger than 18 years at the index date will be considered in the pediatric population.

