Anticoagulation for patients with heart valve replacement or a stent	Heart valve replacement Insertion of coronary stent, bypass anastomosis for heart revascularisation	See codes in Table 4 Z95.1 Z95.5	For stent or aorto-coronary bypass surgery in absence of atrial fibrillation (see Table 4)
General prophylaxis or treatment of a thrombus in any site	Malignancies	C00-C97	In absence of codes in Table 3 or Table 4
Patients with hypercoagulability	Antiphospholipid syndrome	D68.61	In absence of codes in Table 3 or Table 4

* = wild card character indicating additional subcodes under this primary code; ICD-10-CM = International Statistical Classification of Diseases and Related Health Problems, 10th Revision, Clinical Modification, 2014 version. Procedural codes will be refined based on the dictionary system in place in each database

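### Table 4 files complications of coronary bypass grafts under valvular heart disease, so some atrial fibrillation users are wrongly removed from restrictive on-label use

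*Protocol*

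**What the plan says.** Protocol Section 3.5.1 sets two levels of on-label use. The broad level rests on the main code for the indication, which for AF is I48*. The restrictive level narrows it by "excluding patients with conditions for which the medication might not be indicated within the broad definition, e.g., valvular heart disease".

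Table 4 puts the restrictive level into codes. Its valvular heart disease block ends with a row that groups T82.0*, T82.2* and T82.6*. The description that goes with T82.2* is "Mechanical complication of coronary artery bypass graft and biological heart valve graft", and the stated use of the row is "Sub-group of exclusive codes for the restrictive definition within the clinical indication". The table note defines the asterisk as a wildcard for sub-codes. Further down, the same table lists ischaemic heart disease (I20*-I25*) as a secondary code that supports the AF indication.

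Table 5 in Section 3.5.2 has one row headed "Anticoagulation for patients with heart valve replacement or a stent". For valve replacement it sends the reader to Table 4 without naming rows. For stent and bypass it gives Z95.1 and Z95.5 with the condition "For stent or aorto-coronary bypass surgery in absence of atrial fibrillation (see Table 4".

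**The concern.** A bypass graft is not a valve. T82.2* as described covers two different things, and only the biological valve graft belongs in a valvular block. Because the block excludes, the coronary half of the row works against the rest of the plan: a sign of coronary disease, which elsewhere supports the AF indication, takes the user out of restrictive on-label use.

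The restrictive off-label proportion would then contain users who are there through a coding slip and not because of how the drug was prescribed. The unspecific pointer in Table 5 adds to this. If a programmer imports the whole valvular block as valve replacement, T82.2* comes with it, and the condition on absence of AF is written only for stent and bypass. The same patient could be off-label under one half of the Table 5 row and not under the other. Three teams will write code lists from this text, and Section 3.7.1 plans a pooled estimate over their results.

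**Working it through.** **1. The texts side by side, for an AF user whose only code in the valvular block is a bypass-graft complication**

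| Place | Treatment of this user |
|---|---|
| Table 4, I48* | Meets the broad AF definition |
| Table 4, I20*-I25* | Coronary disease supports the indication |
| August 2011 label (Section 3.5.1) | Coronary artery disease is a qualifying factor from age 65 |
| Table 5, stent or bypass | Off-label only if AF is absent, so not off-label here |
| Table 4, T82.2* | Excluded at the restrictive level as valvular |
| Table 5, valve replacement, if the whole Table 4 block is imported | Off-label as valve replacement |

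The December 2013 indication statement no longer names coronary disease, but it does not make it a reason for exclusion either. The last two lines of the table conflict with the others.

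**2. The plan's own precision**

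Table 2 gives 4.4 to 5.6% for 5% off-label use among 5,000 users. The exact (Clopper-Pearson) interval for 250 of 5,000 is 4.41 to 5.64%, which agrees. The half-width is (5.6 - 4.4)/2 = 0.6 points.

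**3. Size of the shift**

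Inputs: 5,000 users per database (Section 3.3.6). Assumed, because the protocol gives no figure: 90% have AF, and 0.1 to 1% of these carry a bypass-graft complication code and no other reason to fail the restrictive level.

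- AF users: 5,000 × 0.90 = 4,500.
- Low end: 4,500 × 0.001 = 4.5 users; 4.5/5,000 = 0.09 points.
- High end: 4,500 × 0.01 = 45 users; 45/5,000 = 0.9 points.

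**4. Shift against precision, true restrictive off-label use 5%, n = 5,000**

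| Share of all users moved | Observed | Exact 95% interval | Contains 5%? |
|---|---|---|---|
| 0.1% | 5.1% | 4.51 to 5.75 | yes |
| 0.5% | 5.5% | 4.88 to 6.17 | yes |
| 1.0% | 6.0% | 5.36 to 6.69 | no |

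Over most of the assumed range the shift is hidden by sampling error. Only near the upper end does it exceed the half-width of 0.6 points.

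**5. Would the planned profile review catch it?**

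Section 3.3.5.1 plans at least 200 CPRD profiles. If these are drawn at random from all users, the expected number affected is 200 × 0.0009 = 0.18 to 200 × 0.009 = 1.8. It cannot be relied on to expose the slip, and it covers one database of three.

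**The case against.** The lists are headed preliminary, and the complete codes are left to the database-specific protocols. Ordinary bypass and stent codes (Z95.1, Z95.5) are not in the Table 4 block, so AF users who carry only those stay on-label under both tables; a reader should not conclude that bypass as such excludes. Table 5's condition on AF is a rule for assigning a non-AF indication and does not promise that every AF user with bypass passes the restrictive level. The shift is assumed, small, and an upper bound, because an affected user may fail anyway through low stroke risk, dose or another valve code. The Appendix 4 diagram of categories could not be consulted here.

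All of this limits the size of the point. It does not justify the row. Section 3 makes the common protocol the basis of each database-specific one, and the Table 4 note promises refinement of procedural codes only, whereas T82.2* is listed as a diagnosis.

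A reader might go further and infer that excluding native-valve disease is also an error, since "Anticoagulation for patients with heart valve replacement or a stent" names only replaced valves and the contraindication in Section 1 concerns prosthetic valves. If 5 to 20% of 4,500 AF users had a native-valve code, that would be 225 to 900 users, or 4.5 to 18 points. The protocol does not support this reading. The labelled indication is non-valvular AF, and excluding valvular disease is the declared purpose of the restrictive level. The Section 3.5.2 list is open ("potential off-label use could include, but is not limited to, the following"), deals with use outside AF, and defines off-label use as use "other than the labelled indications and patient sub-groups given in Section" 3.5.1. A contraindication for prosthetic valves does not define non-valvular.

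**Conclusion.** The point holds for T82.2* and for the pointer in Table 5. Followed as written, Table 4 removes AF users with only a bypass-graft complication from restrictive on-label use under a heading that does not fit them, against its own use of coronary disease and against Table 5.

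The bias in the restrictive off-label proportion is upward and probably small: 0.09 to 0.9 points under the assumptions above. The true size cannot be derived from the protocol. The broad-level proportion uses the AF code alone and is unaffected. The exclusion of native-valve codes is consistent with the label wording and is no part of this finding, and neither are the much larger figures that would go with it.

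**What to change.** 1. In Table 4, limit the T82.2* row to complications of the biological heart valve graft, expressed in each database's coding system. Where that system cannot separate them from bypass-graft complications, drop the row.
2. In Table 5, replace the general pointer with the rows that define heart valve replacement: Z95.2*-Z95.4*, T82.0*, T82.6* and the valve-graft part of T82.2*.
3. Optional, as an aid to interpretation: at the restrictive level, show AF users excluded for a replaced valve and those excluded only for a native-valve code on separate lines.

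The cost is an edit to two code lists before the database-specific protocols are final, plus one table line if the third item is taken up. No new data are needed.

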3.5.2 Off-label use definition

The definition of off-label use of oral dabigatran etexilate outside AF will be based on the use for a disease or medical condition other than the labelled indications and patient sub-groups given in Section [3.5.1](#). The dabigatran indications approved at the time of the index date will be used to define off-label use for each new user identified in the study period. In the absence of labelled indications, potential off-label use could include, but is not limited to, the following:

- General thrombosis prophylaxis other than hip and knee orthopaedic surgery.
- Treatment of deep vein thrombosis (DVT) and pulmonary embolism (PE) and prevention of recurrent DVT and PE in adults (CHMP opinion 25 April 2014), until Commission Decision
- Anticoagulation for patients with heart valve replacement or a stent.
- General prophylaxis or treatment of a thrombus in any site.
- Patients with hypercoagulability (e.g., factor V Leiden thrombophilia).

A preliminary list of ICD-10-CM codes to identify these conditions is provided in [Table 5](#). The final list will be included in the detailed, database-specific study protocol. In addition, the set of algorithms to be used as proxies for identification of potential clinical indications will be defined and described in the detailed, database-specific study protocol. These proxies will be based on codes for the presence of certain diseases and clinical conditions and the use of certain medications (e.g., use of other oral anticoagulants).

Because dabigatran etexilate has been approved for use only in adults, any identified use in the pediatric groups of age will be considered off-label. New users of dabigatran etexilate aged younger than 18 years at the index date will be considered in the pediatric population.

The proportion of users with each of the contraindications, including those based on comedication, disease, or severity of conditions, such as patients with severe renal impairment, will be also described. In those databases with laboratory test results available, severe renal impairment will be defined as creatinine clearance < 30 mL/min from directly recorded information of the estimated renal function, as available. For those patients with serum creatinine levels and patient weight available, we might estimate glomerular filtration rate by using the Cockcroft-Gault equation and/or the CKD-EPI equation [[R13-5416](#)]. However, it is important to be aware that actual values of laboratory test results will be inconsistently recorded in most databases and data will be limited. We will also capture those patients with ICD-10-CM codes for advanced renal disease—N18.4-N18.6, chronic kidney disease, stages 4 and 5 (severe), and end-stage renal disease—as available in each database according to the coding system and version in place.

Given the different recommended dosage regimens in both the approved and the new indications, new users of dabigatran etexilate will be described according to dose categories, but dose will not be included in the study definition of off-label use based on the first level of on-label indications.

Dose will be incorporated in the definition of off-label use based on the second level, which is a more restrictive definition of on-label use (see [Appendix 4](#)). In addition, the proportion of new users within the primary VTE prevention subgroup with one or more follow-up prescriptions after the recommended treatment duration will be described. The follow-up prescriptions will be assessed in the 90-day time window after the index prescription..

Table 5 Preliminary list of diagnoses and corresponding ICD-10-CM codes for identification of potential off-label clinical indications of dabigatran etexilate

Disease/condition or procedure	ICD-10-CM description	ICD-10-CM code	Use of codes in off-label indication definitions
Treatment or secondary prevention of venous thromboembolism	Venous thrombosis Pulmonary embolism	I80.1*, I80.2*, I82.3* I26*	
General thrombosis prophylaxis other than hip and knee orthopaedic surgery	Injuries to the knee and lower leg Fracture of femur	S80*-S89* S72*	In the absence of codes for hip or knee orthopaedic surgery (see Table 3)
Anticoagulation for patients with heart valve replacement or a stent	Heart valve replacement Insertion of coronary stent, bypass anastomosis for heart revascularisation	See codes in Table 4 Z95.1 Z95.5	For stent or aorto-coronary bypass surgery in absence of atrial fibrillation (see Table 4)
General prophylaxis or treatment of a thrombus in any site	Malignancies	C00-C97	In absence of codes in Table 3 or Table 4
Patients with hypercoagulability	Antiphospholipid syndrome	D68.61	In absence of codes in Table 3 or Table 4

* = wild card character indicating additional subcodes under this primary code; ICD-10-CM = International Statistical Classification of Diseases and Related Health Problems, 10th Revision, Clinical Modification, 2014 version. Procedural codes will be refined based on the dictionary system in place in each database

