3.5.1 On-label use definition

On-label use is when a medication is used as described in the approved drug label. As of 1 August 2011, the EMA-approved indications for Pradaxa were as follows:

- Primary prevention of venous thromboembolic events in adult patients who have undergone elective total hip replacement surgery or total knee replacement surgery.
- Prevention of stroke and systemic embolism in adult patients with non-valvular atrial fibrillation with one or more of the following risk factors:
 - Previous stroke, transient ischaemic attack, or systemic embolism (SEE)

- Left ventricular ejection fraction < 40%
- Symptomatic heart failure, New York Heart Association (NYHA) Class 2 or higher
- Age \geq 75 years
- Age \geq 65 years associated with one of the following: diabetes mellitus, coronary artery disease, or hypertension

A revision of this indication statement was submitted for approval in the EU in September 2013. The revision became effective in December 2013, introducing the following modified indication statement: “Prevention of stroke and systemic embolism in adult patients with non-valvular atrial fibrillation (NVAF) with one or more risk factors, such as prior stroke or transient ischemic attack (TIA); age \geq 75 years; heart failure (NYHA Class \geq II); diabetes mellitus; hypertension.”

The indication application for treatment or secondary prevention of venous thromboembolism EMA/H/C/00829/II/48G obtained a positive CHMP opinion on 25 April 2014 with the following indication statement: “Treatment of deep vein thrombosis (DVT) and pulmonary embolism (PE), and prevention of recurrent DVT and PE in adults.” During the study period, use associated with these indications will be considered off-label use until Commission Decision. The definition of on-label use will have to consider regulatory label changes that have occurred during the product life cycle with respect to indication and also to contraindications (e.g., addition of dronedarone use to the list of contraindications since 30 August 2012). Therefore on-label use will be defined considering the index date and the appropriate label indication and contraindication applicable during the time period comprising the index date.

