3.6.1 Assessment of clinical history and comorbidities

The presence of the following diseases and conditions of interest will be assessed based on the total cumulative clinical history or the baseline period for each patient at the index date, as available in each database:

- Chronic diseases, particularly those related to atrial fibrillation, including cardiovascular and cerebrovascular diseases, hypertension, and diabetes mellitus.
- Diseases or conditions related to the potential off-label use of dabigatran etexilate such as other heart valve replacement, deep venous thrombosis, pulmonary embolism, and disorders of coagulation (i.e., antiphospholipid syndrome).
- Surgical or percutaneous procedures related to the potential off-label use of dabigatran etexilate such as coronary revascularisation procedures or surgery, general or orthopaedic surgery other than hip and knee orthopaedic surgery. The presence of lower limb fractures will also be evaluated.

A complete list of comorbidities will be developed and included in the detailed, database-specific study protocol.

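### The off-label prophylaxis category exempts all hip and knee orthopaedic surgery, which is wider than the labelled elective total replacement, and two patient groups are misplaced as a result

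*Protocol*

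**What the plan says.** - **Label.** Section 3.5.1 gives the orthopaedic indication as "Primary prevention of venous thromboembolic events in adult patients who have undergone elective total hip replacement surgery or total knee replacement surgery". The synopsis and Section 1 carry the same indication.
- **General rule.** Section 3.5.2 bases off-label use on "use for a disease or medical condition other than the labelled indications and patient sub-groups given in Section" 3.5.1, and introduces its list with "potential off-label use could include, but is not limited to, the following".
- **Category.** The first item of that list is "General thrombosis prophylaxis other than hip and knee orthopaedic surgery". The synopsis and the row name in Table 5 use the same phrase.
- **Table 5 row.** The codes are S72* and S80*-S89*, described as "Injuries to the knee and lower leg Fracture of femur". The row applies "In the absence of codes for hip or knee orthopaedic surgery (see Table 3").
- **Table 3.** The surgery codes are Z96.64*, "Presence of artificial hip joint", and Z96.65* for the knee. Both are primary codes for the broad on-label definition. The only exclusion listed for the restrictive definition is venous thromboembolism. Neither the title nor the rows mention elective surgery.
- **Section 3.6.1.** The procedures related to off-label use include "general or orthopaedic surgery other than hip and knee orthopaedic surgery". Lower limb fractures are to be evaluated as well.

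**The concern.** An off-label category that borders a labelled indication should begin where the label ends. Here the label ends at elective total replacement, but the category begins only outside hip and knee orthopaedic surgery altogether. Between the two lies prophylaxis after other hip or knee operations, including replacements that are not elective. That is the closest neighbour of the labelled orthopaedic use, and it is off-label use outside atrial fibrillation, which Section 1 says the regulator asked about.

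The wording matters because use is classified by code. Sections 2 and 3.3.5 rely on recorded indications or on proxies built from code sets. Section 3.7.1 reports the off-label proportion as the main result and breaks it down by type of indication. Section 3 makes this common protocol the basis for three database-specific protocols in different coding systems, so an over-wide concept can be implemented differently in each and carried into the pooled estimate.

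**Working it through.** The protocol gives no figure on this point, so the check sets the definitions side by side and traces cases through Tables 3 and 5. Each case assumes no atrial fibrillation code and no other listed code.

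**Scope of the exemption**

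| Place | What is exempt from off-label |
|---|---|
| Section 3.5.1 (the label) | elective total hip or total knee replacement |
| Synopsis, Section 3.5.2, Section 3.6.1 | all hip and knee orthopaedic surgery |
| Table 5, row name | all hip and knee orthopaedic surgery |
| Table 5, condition as it operates through Table 3 | any patient with Z96.64* or Z96.65* |

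**Cases**

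1. *Femur fracture or knee injury, operated on without replacement.* S72* or S80*-S89* is present and no Table 3 code is present. The condition is met, so the patient is in the off-label row. This is correct.
2. *Hip or knee operation that is not a replacement and not for injury.* No code in the prophylaxis row applies. The row for a thrombus in any site does not help, since it carries only malignancy codes (C00-C97). Section 3.6.1 leaves the operation out of the off-label-related procedures. The patient reaches no Table 5 row and no Table 3 row. Section 3.3.5 expects some courses to have no clear indication, and this patient may look the same as those.
3. *Joint replacement after a femur fracture.* S72* is present, but Z96.64* is present too. That code switches off the S72* row and is a primary code for broad on-label use. Table 3 has no elective restriction, so the patient is counted as broad on-label although Section 3.5.1 requires elective surgery. The one restrictive exclusion in Table 3, venous thromboembolism, does not remove the patient either.

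**Direction of the effect**

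Let n be the number of new users, k the true number off-label and x the number misplaced as in cases 2 and 3, with 0 < x ≤ k < n.

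- Misplaced users kept in the denominator: (k − x)/n, which is below k/n.
- Misplaced users dropped as unknown: (k − x)/(n − x), which is also below k/n.

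The estimate falls either way. The protocol gives no frequency for either group, so x cannot be filled in.

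**The case against.** The strongest reply is that the general rule already settles the matter. Any use outside the labelled indications is off-label, the list is open, and Tables 3 and 5 are preliminary, with final codes and algorithms left to the database-specific protocols. Section 3.3.5.1 also provides for review of at least 200 CPRD profiles, after which algorithms may be modified. In principle this stands: both groups are off-label under the rule. It does not settle the practice. A user is found off-label through a recorded indication or a code-based proxy. In case 2 the proxy has no code, and in case 3 it points to the wrong side. The codes are preliminary, but the category wording is the concept that the database teams are asked to code. The profile review covers only one of the three databases.

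A second reply is that the first level of on-label use is meant to be broad. That is fair for case 3 at that level. But Table 3 has no elective restriction for the restrictive level either.

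A reader might infer that prophylaxis after every hip or knee operation other than replacement falls outside all off-label rows. The documents do not support this. The Table 5 condition points to Table 3, whose only surgery codes are for artificial joints, so case 1 is captured, and Section 3.6.1 evaluates lower limb fractures. A reader might add that case 1 patients will be lost once procedure codes are added under the Table 3 footnote. That could happen if a team coded the Table 5 condition literally. However, Table 3 concerns replacement only, and the footnote most naturally means local codes for those same rows.

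**Conclusion.** The point holds in a limited form. The category wording contradicts the protocol's own on-label definition in four places. Two groups are affected: non-injury, non-replacement hip or knee surgery, and replacement after a femur fracture. Both can bias the off-label proportion downward.

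The size cannot be given. A reader might assume that such users make up 1 to 2% of 5,000 and subtract that from the off-label percentage. Nothing in the protocol supports this: it gives no frequency of such surgery, and case 1 patients are not lost. Section 3.1 also expects even the labelled orthopaedic use to be concentrated mainly in hospital, so few of these users may appear in primary care data.

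The conclusion assumes that Tables 3 and 5 are carried into the database-specific protocols broadly as they stand, and that users without a listed code are not otherwise assigned to off-label use. The diagram in Appendix 4 is not in the text reviewed here and could bear on the second assumption. The contradiction in wording does not depend on either. It should be corrected, chiefly because this is cheap and avoids three different readings.

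**What to change.** 1. In the synopsis, Section 3.5.2, Table 5 and Section 3.6.1, replace the exemption by *other than elective total hip or total knee replacement*.
2. In Table 5, make the condition *in the absence of an elective total hip or knee replacement (Table 3)*. State in both tables that a replacement recorded with an acute S72* fracture as its reason neither switches off the off-label row nor counts as on-label. A condition that named replacement without *elective* would leave case 3 as it is.
3. Add non-replacement hip and knee procedure codes to Table 5 and to the off-label-related procedures in Section 3.6.1.

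The cost is wording in four places and some extra procedure codes in the database-specific lists. No new data source is needed. Elective status may be only partly identifiable in some databases: Cegedim, for example, holds no hospitalisation data. Each database-specific protocol should say how far it can be determined and how undetermined cases are reported.
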